#### 4. ANALYSIS SETS

Four analysis sets will be used for the study: Enrolled Set, Safety Set, Efficacy Set (referred respectively as the Enrolled Population, Safety Analysis Population, and Efficacy Analysis Population in Section 11.3 of the protocol), and Per Protocol Set.

Analysis Set	Description
Enrolled Set	The Enrolled Set will consist of all participants enrolled (signed informed consent and met inclusion/exclusion criteria) into the study irrespective of whether they received andexanet or not.
Safety Set (SS)	The Safety Set will consist of all participants enrolled and treated with any amount of andexanet.
Efficacy Set	The Efficacy Set will include all enrolled participants who receive any amount of andexanet treatment, undergo surgery, and have a baseline anti-fXa activity analyzed by central laboratory at or above the evaluability threshold (75 ng/mL for apixaban and rivaroxaban, 40 ng/mL for edoxaban, and 0.25 IU/mL for enoxaparin).
Per-Protocol Set (PPS)	The Per Protocol Set will include all participants meeting the definition of the Efficacy Set with no important protocol deviations that could potentially impact the accuracy/interpretability of the primary or secondary efficacy endpoints. The Per Protocol Set exclusion criteria will be finalized prior to database lock.

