## **5.6. Safety Analyses**

Safety will be assessed by examining the following endpoints and analyzed using the Safety Set:

- Adverse events (AEs) (including serious adverse events [SAEs]), vital signs, and clinical laboratory measurements

- TEs within 30 days of enrollment, including those suspected and confirmed by adjudication
- Centrally-adjudicated deaths within 30 days of enrollment, including all-cause mortality and cardiovascular mortality
- Antibodies to FX, FXa, and andexanet

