#### 5.6.2.2. TEAEs and SAEs by System Organ Class (SOC) and Preferred Term

The number and percentage of TEAEs will be presented by SOC and Preferred Term. At the participant level, participants are counted once in each SOC and Preferred Term. Percentages

will be based on the total number of treated participants. SOC's will be listed in alphabetical order, and Preferred Terms within each SOC will be sorted by descending frequency of participants reporting the event.

SAEs, TEAEs leading to withdrawal of study drug, and TEAEs occurring in  $\geq 5\%$  of patients will be tabulated by SOC and Preferred Terms in a similar manner.

Additional tables summarizing TEAEs by surgery type and baseline FXa inhibitor may also be provided.

TEAEs and treatment-emergent related adverse events will also be tabulated but at the Preferred Term level only, for number of participants as well as for number of events, with Preferred Terms sorted by descending frequency.

Participants with events during the screening period (Pre-treatment adverse events [PTAEs]) will be presented in a data listing.

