## **6.2. Appendix 2: Study and Participant Characteristics**

### **6.2.1. Protocol Deviations**

Protocol deviations will be tabulated for the Safety and Efficacy Sets and will be presented for overall and for major deviations.

Deviations categories will include the following:

- Eligibility and Entry Criteria
- Investigational Product Compliance
- Concomitant Medication Criteria
- Informed Consent Criteria
- Laboratory Assessment Criteria

- Visit Schedule Criteria
- Study Procedures Criteria
- Serious Adverse Event Criteria
- Source Document Criteria
- Other Criteria

Major deviations are a subset of protocol deviations that may significantly impact the completeness, accuracy, and/or reliability of key study data or that may significantly affect participant's rights, safety, or well-being. Major deviation criteria will be determined prior to database lock.

Details around protocol deviations specific to the primary efficacy endpoints are provided as follows:

- Protocol deviations related to the evaluation of hemostatic efficacy will be considered significant (major) if the adjudication decision is impacted by the deviation
- The majority of protocol deviations regarding the hemostatic efficacy endpoints will be considered by the EAC. Any protocol deviations not considered by the EAC may be individually considered within the analysis of the data and discussed in the Clinical Study Report (CSR)

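### Section 4 ties the Safety and Efficacy Sets to a definition of enrolment that requires the entry criteria to be met, so on a literal reading a participant dosed but later found ineligible is left out of the summary tables

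*SAP*

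**What the plan says.** SAP Section 4 defines the Enrolled Set as "all participants enrolled (signed informed consent and met inclusion/exclusion criteria) into the study irrespective of whether they received andexanet or not". The other sets rest on that term:

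- Safety Set: "The Safety Set will consist of all participants enrolled and treated with any amount of andexanet".
- The population for efficacy is worded in a similar way: "The Efficacy Set will include all enrolled participants who receive any amount of andexanet treatment, undergo surgery", with a further condition on the baseline anti-fXa level.
- Per Protocol Set: "all participants meeting the definition of the Efficacy Set with no important protocol deviations". The addendum of 8 April 2022 (item 1) removes this set and leaves the other three definitions as they were.

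Section 5.6 applies the Safety Set throughout: "Safety will be assessed by examining the following endpoints and analyzed using the Safety Set".

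Two other sections describe who is in these sets or in the denominator. Section 6.2.1 says "Protocol deviations will be tabulated for the Safety and Efficacy Sets", and the first deviation category it lists is eligibility. Section 5.6.2.2 says that adverse event percentages "will be based on the total number of treated participants".

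**The concern.** A safety population is normally fixed by exposure alone. Here it carries a second condition, inherited from the parenthesis in the Enrolled Set definition. A person who was given andexanet and turned out not to meet a criterion would then fall outside the Safety Set, and that person's adverse events would be missing from the numerators and the person from the denominators. The Efficacy Set inherits the same condition.

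Such a finding after dosing is plausible in this setting. Section 1.2 sets limits on the time from the last anticoagulant dose, or from a local laboratory sample, to the start of surgery, and it has the bolus completed before the first incision. Whether those limits were kept is known only once the participant has been exposed. Whether each limit is formally an inclusion criterion is a matter for the protocol, which was not available for this check.

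**Working it through.** The plan gives no figure on this point, and its sample-size statement in Section 3 does not depend on it. The check is therefore a comparison of sections, followed by an illustration of size.

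**Step 1. Set membership under the two possible readings of the enrolment definition.**

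| Participant | Literal: criteria actually met | Entry gate: judged eligible at entry |
|---|---|---|
| Eligible and dosed | Enrolled, Safety | Enrolled, Safety |
| Passed at entry, dosed, later found ineligible | none | Enrolled, Safety, and Efficacy if its other conditions hold |
| Consented, rejected at screening, not dosed | none | none |

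The readings differ only in the second row. No sentence in the SAP says which one applies.

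**Step 2. Test each reading against the other sections.**

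- Section 6.2.1: under the literal reading, the eligibility category must be empty in both sets for which it is tabulated. Under the entry-gate reading it can be filled. This is a real conflict with the literal wording.
- Section 5.6.2.2: under the literal reading, the number treated exceeds the Safety Set by the number dosed while ineligible, so Sections 5.6 and 5.6.2.2 give different denominators. Under the entry-gate reading they agree.
- Section 5.2: screen failures are counted first, and failures of entry criteria are counted separately by protocol version. This suggests that some entered participants were expected to fail a criterion, but it is weaker evidence because the text does not say that they were entered.

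**Step 3. Size, as an illustration.** The addendum gives 10 enrolled. The SAP gives neither the number dosed nor the number dosed while ineligible. Assume N dosed, 1 of them ineligible, and x of the N with a given event.

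- The ineligible participant had the event: shift = x/N − (x−1)/(N−1) = (N−x)/[N(N−1)], and the table understates the rate.
- The ineligible participant did not: shift = x/(N−1) − x/N = x/[N(N−1)], and the table overstates it.

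With N = 10 the divisor is 10 × 9 = 90:

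| x | Event in the ineligible participant? | All dosed | Literal Safety Set | Shift (points) |
|---|---|---|---|---|
| 0 | no | 0/10 = 0% | 0/9 = 0% | 0 |
| 1 | yes | 1/10 = 10.0% | 0/9 = 0% | 9/90 = 10.0 |
| 1 | no | 1/10 = 10.0% | 1/9 = 11.1% | 1/90 = 1.1 |
| 2 | yes | 2/10 = 20.0% | 1/9 = 11.1% | 8/90 = 8.9 |
| 5 | yes | 5/10 = 50.0% | 4/9 = 44.4% | 5/90 = 5.6 |
| 10 | yes | 10/10 = 100% | 9/9 = 100% | 0 |

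The range is 0 to 10 points. At the planned size, taking N = 100 dosed, the divisor is 100 × 99 = 9,900 and the maximum is 99/9,900 = 1.0 point.

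On the literal reading, the 10 enrolled all met the criteria, so an ineligible dosed person would be an eleventh. If all 10 were dosed as well, N = 11 and the maximum is 1/11 − 0/10 = 9.1 points, which is of the same order.

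**The case against.** The strongest reply is that nothing in the SAP expressly removes a dosed participant. The parenthesis can be taken as the gate that separates the enrolled from screen failures, whom Section 5.2 draws from everyone who signed consent. Section 6.2.1 then shows that the authors meant violators to stay, and the treated denominator in Section 5.6.2.2 is simply shorthand for the Safety Set. Section 6.5.1 lists no change from the protocol to the Enrolled or Safety definitions, so the protocol may settle the meaning. The addendum (item 15) has also withdrawn the deviation table. This stands as evidence of intent. It does not make the definition say what was intended, and two programmers working from different sections could still produce different denominators.

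Three stronger readings are tempting and are not supported:

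- *Exposed people and their events vanish from the report.* Section 5.1 promises listings at a minimum, and the addendum confines its changes to summary tables. The possible loss is from those tables.
- *The Efficacy Set becomes a hidden per-protocol set, or the Per Protocol Set becomes redundant.* Even read literally, the Efficacy Set keeps participants with dosing, visit, laboratory, medication and procedure deviations. Eligibility is one of ten categories in Section 6.2.1, so the Per Protocol Set kept a function of its own. This is not a contradiction.
- *Each ineligible participant moves a rate by about 10 points.* That is the maximum, and it assumes that 10 were dosed, whereas the Enrolled Set can include people who received no andexanet.

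**Conclusion.** The point holds as a defect of definition. Taken at its word, Section 4 leaves a dosed but ineligible participant out of every analysis set. That conflicts with Section 6.2.1 and sits poorly with Section 5.6.2.2. The other reading, eligible as judged at entry, would remove the problem but is not stated.

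A reader might infer that participants were in fact dropped from this trial's tables. The SAP does not show that anyone was dosed while ineligible, so the actual effect may be nil. If there was one such person among 10 dosed, an event rate could shift by 0 to 10 points in either direction, depending on how many had the event and whether that person was among them. The corresponding range for 100 dosed is 0 to 1 point.

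**What to change.** Make two changes in Section 4:

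1. Define the Safety Set as everyone who received andexanet in any quantity, regardless of eligibility.
2. Define enrolment as signed consent plus the site's decision at entry that the participant was eligible, and state that an eligibility deviation identified later does not remove a participant from the Enrolled or Efficacy Set. The Efficacy Set's conditions on treatment, surgery and baseline anti-fXa level stay as they are.

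Sections 5.6, 5.6.2.2 and 6.2.1 then agree without further editing. The cost is two sentences and a check of the population flags, with no new data and no effect on the sample size. If tables have already been produced, compare the list of everyone dosed with the Safety Set and report any difference, or its absence, in the study report.

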## 5. STATISTICAL ANALYSES

### 5.1. General Considerations

For continuous variables, the number of observations, mean, median, standard deviation, first quartile (Q1), third quartile (Q3), interquartile range (IQR), and minimum and maximum values, will be presented. For categorical variables, unless specified otherwise, counts and percentages will be based upon number of participants with non-missing values in the analysis set.

Confidence intervals will be provided for the mean for all continuous efficacy variables except for percent change from baseline variables, for which CIs for the median will be generated. For binary variables, normal-approximated CIs for the binomial proportion will be provided unless stated otherwise.

No hypothesis testing will be conducted in this single-arm, proof-of-concept study. All CIs will be 2-sided and reported at the 95% confidence level unless stated otherwise.

Summary statistics will be provided for each time point/visit at which the variable is collected unless otherwise stated. Visit/time point windows will not be employed. See Section 6.7 for the schedule of study activities.

Summary table(s) will be generated for all data described in this SAP unless otherwise noted. At a minimum, data listings will be provided for these data.

In general, no missing data imputation will be performed unless stated otherwise.

It is anticipated that statistical summaries will be performed using Statistical Analysis Software (SAS®) Version 9.4 (SAS Institute, Inc., Cary, NC, USA) or higher. Additional software may be used for the production of graphics and for statistical methodology not available in SAS.

### 5.2. Study Participants

The number of participants screened, and the number and percentage of screen failures along with the reason for screen failure will be reported, where screened participants are those who signed the informed consent.

The number of enrolled participants (Total), and the number of participants in the Safety and Efficacy Analysis Sets will be tabulated. Within each analysis set, the number of participants excluded from the Enrolled Set, along with the reason for exclusion will be tabulated.

Enrollment by region (North America, European Union, and Asia), country, and site will be tabulated for the Enrolled Set. Additionally, participant enrollment by protocol version will be tabulated. Finally, the number of participants who failed inclusion/exclusion criteria will be tabulated and along with the protocol version under which the failure occurred.

An accounting of study participant disposition will be tabulated for the Enrolled Set and will include the number of participants who completed the study (including the 30-Day Follow-up Visit), discontinued early, and the reason for discontinuation from the study. Descriptive statistics will be provided for study duration (days).

### 5.3. Primary Endpoint Analysis

The primary endpoint analysis will be performed on the Efficacy Set unless stated otherwise.

#### 5.3.1. Endpoint

The primary efficacy endpoint is the achievement of effective hemostasis, as determined by the investigator's assessment of intraoperative hemostasis using a pre-specified 4-point scale (Table 2) and confirmed by adjudication by an independent EAC.

**Table 2: Intraoperative Hemostasis Categories**

Category	Definition
Excellent	Normal hemostasis during the procedure
Good	Mildly abnormal hemostasis as judged by quantity or quality of blood loss (eg, slight oozing from surgical wounds)
Moderate	Moderate abnormality in intraprocedural hemostasis (eg, controllable bleeding) but no need for additional systemic procoagulant products *
Poor	Severe hemostatic abnormality during the procedure (eg, severe refractory hemorrhage) and need for additional systemic procoagulant products *

\* Tranexamic acid excluded.

The hemostasis evaluation would exclude unexpected blood loss due to surgical complications that may cause uncontrolled bleeding, such as unintended injury of a major vessel or parenchymal tissue.

For each participant, hemostasis will be considered to be effective if the intraoperative hemostasis category is 'Excellent' or 'Good,' and ineffective if the intraoperative hemostasis category is 'Moderate' or 'Poor.' A participant will be deemed non-evaluable if s/he meets the criteria specified in the EAC Charter (see Section 5.3.2).

#### 5.3.2. Main Analytical Approach

The number of participants achieving effective hemostasis will be tabulated. An exact Clopper-Pearson 95% CI for the proportion of participants with effective hemostasis will be provided.

All participants in the Efficacy Set will be included in the primary analysis except for certain EAC adjudicated cases as described below.

Cases where it is determined that there is insufficient information, or where it is not otherwise possible to properly assess the effect of treatment, will be classified by the EAC as 'non-evaluable due to administrative reasons' (eg, participant transferred to another facility for administrative purposes) or 'non-evaluable due to clinical reasons' (eg, participant died).

Participants whose hemostatic efficacy is 'non-evaluable due to administrative reasons' will be excluded in all applicable efficacy analyses.

Participants whose hemostatic efficacy is 'non-evaluable due to clinical reasons' will be considered as having moderate/poor hemostatic efficacy and included in the denominator in the primary analysis as having ineffective hemostasis; but treated as not having an effective hemostasis value and thus excluded in the denominator in a sensitivity analysis (Section 5.3.3).

### 5.3.3. Sensitivity Analysis

To evaluate the sensitivity of the primary efficacy analysis, the primary efficacy analysis will be repeated with the following changes separately:

- Exclude the hemostatic efficacy values deemed ‘non-evaluable due to clinical reasons’ by the EAC (which are otherwise automatically included as ineffective hemostasis values in the primary efficacy analysis in Section 5.3.2)
- Include only participants in the Per Protocol Set

## 5.4. Secondary Endpoint Analysis

The secondary endpoint analysis will be performed on the Efficacy Set unless stated otherwise.

### 5.4.1. Endpoint

Anti-fXa activity will be measured using plasma samples to assess the ability of andexanet to reverse the anticoagulant effect of FXa inhibitors. Anti-fXa activity will be measured by a modified chromogenic assay. These assays will be performed at a central laboratory.

The secondary efficacy endpoint is the percent change in anti-fXa activity from baseline to the evaluation period nadir. The evaluation period starts from the end of the andexanet bolus and ends at the end of the andexanet infusion. The baseline measurement will be the last value obtained prior to andexanet treatment. Anti-fXa activity will be measured using plasma samples to assess the ability of andexanet to reverse the anticoagulant effect of FXa inhibitors. Anti-fXa activity will be measured by a modified chromogenic assay. These assays will be performed at a central laboratory.

### 5.4.2. Main Analytical Approach

The secondary endpoint will be assessed with a 2-sided 95% non-parametric CI for the median. Percent change will be calculated as  $100\% \times (\text{change from baseline to nadir/baseline})$ . Patients who do not have at least 1 anti-fXa activity level within the evaluation period will have percent decrease imputed as 0.0% (i.e., using the baseline value as the nadir value).

### 5.4.3. Sensitivity Analysis

The same analysis described in Section 5.4.2 will be repeated using the Per Protocol Set.

## 5.5. Exploratory Endpoint Analysis

All exploratory endpoint analyses will be performed on the Efficacy Set.

The following efficacy endpoints will be analyzed as exploratory:

- Relationship between intraoperative hemostasis and anti-fXa activity
- Anti-fXa activity as measured by additional parameters, including, but not limited to: on-treatment nadir, absolute change from baseline to on-treatment nadir, number of participants with percent reduction from baseline > 80%

- Reversal of anticoagulant effect as measured by thrombin generation (TG) parameters (with endogenous thrombin potential [ETP] as the primary measure)
- Occurrence of receiving 1 or more red blood cell (RBC) transfusions from start of the andexanet bolus through 12 hours after the end of surgery
- The number of RBC units transfused per participant from the start of the andexanet bolus through 12 hours after the end of surgery
- The use of non-RBC, non-platelet blood products and/or hemostatic agents (both systemic and topical) through 12 hours after the end of surgery
- Observed amount of intraoperative blood loss
- Difference between observed blood loss and predicted blood loss
- Transfusion-corrected change in hemoglobin from baseline to nadir within 12 hours after the end of surgery
- Time from the signing of informed consent to the start of surgery
- Time from clinical presentation at treatment facility to the start of surgery
- Length of index hospitalization, assessed at the Day 30 Visit
- Time hospitalized in a post-anesthesia care unit (PACU), assessed at the Day 30 Visit
- Time hospitalized in an intensive care unit (ICU), assessed at the Day 30 Visit
- Length of surgery
- Total time in the operating room (OR)
- Occurrence of re-hospitalization, within 30 days of enrollment, including length of re-hospitalization (through 30 days post enrollment)
- Occurrence of post-surgical major bleeding, as defined by International Society on Thrombosis and Hemostasis (ISTH) criteria (see Protocol Section 4.1), within 12 hours after the start of the initial surgery
- Occurrence of re-operations for bleeding, including for surgical wound hematomas, within 12 hours after the end of the initial surgery
- Change from baseline in tissue factor pathway inhibitor (TFPI) activity post-administration of andexanet
- Change from baseline in anti-IIa activity (only participants taking enoxaparin)

#### **5.5.1. Relationship Between Anti-fXa Activity and Hemostasis**

Anti-fXa activity (percent change from baseline to on-treatment nadir) will be summarized by achievement of hemostatic efficacy (effective versus ineffective).

#### **5.5.2. Anti-fXa Activity – Absolute and Percent Change from Baseline**

Absolute change (including on-treatment nadir) and percent change from baseline at each time point will be summarized by FXa inhibitor (apixaban, rivaroxaban, edoxaban [ng/mL];

enoxaparin [IU/mL]). Furthermore, 95% CIs for the mean (absolute change) and the median (percent change) will be provided. On-treatment nadir is the minimum anti-fXa activity from the end of andexanet bolus to the end of the andexanet infusion.

In addition, the number and percent of participants with percent reduction from baseline at any time point > 80% will be tabulated and 95% CI for the proportion will be presented.

### **5.5.3. Reversal of Anticoagulant Effect - Thrombin Generation**

Five parameters related to TG are measured: endogenous thrombin potential (ETP [nM\*min]), peak height (nmol), time to peak height (min), lag time (min), and velocity index (nmol/min). ETP is prospectively identified as the primary measure for TG.

For each of the 5 parameters, descriptive statistics and CIs will be provided for baseline and change from baseline values at each applicable time point/visit (Section 6.7).

